## **4.2. Definition of Study Drugs**

Only the investigational product BCX7353 will be used as a study drug in this trial. Two dose levels will be examined.

## **4.3. Sample Size Considerations**

### **4.3.1. Sample Size Justifications**

No sample size calculations were conducted for this open-label, long-term safety study. The purpose of the study is to characterize the safety profile of 110 and 150 mg daily doses of BCX7353.

Approximately 225 subjects (approximately 110 subjects at each dose level) may be enrolled in this study, to allow continued access to BCX7353 following a subject's participation in a prior BCX7353 study, or to provide access to BCX7353 for additional subjects who, in the opinion of the Investigator, are expected to benefit from treatment with an oral treatment for the prevention of angioedema attacks.

## **4.4. Allocation to Treatment Group**

This is an open-label study. Subjects will be centrally allocated to 1 of 2 treatment groups:

- Group 1: BCX7353 110 mg administered orally once daily (QD)
- Group 2: BCX7353 150 mg administered orally QD

Sites will request a treatment allocation for eligible subjects in the Interactive Response System, preferably after all baseline assessments to reconfirm eligibility have completed. If required by site procedures (ie, dispensing of allocated study drug must occur through a pharmacy), the treatment allocation request may be made on the business day prior to the planned baseline visit.

Version 1 of the protocol included only the BCX7353 150 mg dose for those in previous BCX7353 clinical trials. As Version 1 of the protocol only utilized the 150 mg dose, sites initiated under protocol Version 1 have all subjects allocated to the 150 mg dose. Protocol Version 2 allowed for subjects to be treated with either the 110 or 150 mg dose. Protocol Version 3 broadened the inclusion criteria to allow for inclusion of subjects who had not previously participated in clinical trials of BCX7353. Sites initiated under Protocol Versions 2 or 3, or who were initially included under Protocol Version 1 and later changed versions, may have subjects allocated to 150 or 110 mg.

No changes to the allocation scheme were made in Protocol Versions 4 and 5.

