2. SYNOPSIS

Name of Sponsor/Company: BioCryst Pharmaceuticals, Inc.
Name of Investigational Product: BCX7353
Name of Active Ingredient: (R)-1-(3-(aminomethyl)phenyl)-N-(5-((3-cyanophenyl)(cyclopropylmethylamino)methyl)-2-fluorophenyl)-3-(trifluoromethyl)-1H-pyrazole-5-carboxamide
Title of Study: An open-label study to evaluate the long-term safety of daily oral BCX7353 in subjects with Type I and II hereditary angioedema
Study center(s): Protocol Versions 1.0-4.0, 7.0: Multiple study centers in Asia-Pacific, Europe, Israel, and South Africa Protocol Versions 5.0, 6.0, 8.0, 9.0: Multiple centers in the United States (US) only
Principal Investigators: Global Principal Investigator: [name] [name], DSc United States Principal Investigator: [name]
Phase of development: 2
Primary Objective: 
To evaluate the long-term safety and tolerability of daily dosing of oral BCX7353 in subjects with hereditary angioedema (HAE) Secondary Objective: 
To assess the effectiveness (ie, HAE attack frequency, severity and disease activity over time) of BCX7353 during long-term administrationTo evaluate quality of life (QoL) during long-term administration of BCX7353To evaluate subject's satisfaction with medication during long-term administration of BCX7353

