Methodology: 
This is a single-arm, open-label study to evaluate the long-term safety and effectiveness of orally administered BCX7353 in subjects with HAE who are expected to derive benefit from an oral treatment to prevent angioedema attacks.
 
Subjects who meet the inclusion and exclusion criteria will be enrolled into the study for up to 96 weeks. Subjects enrolled under protocol versions 6.0 and 9.0 will receive BCX7353 150 mg administered orally once daily (QD).
 
Study visits will occur at Screening, Baseline/Day 1, at Weeks 4, 12, 24, 48, 72, and 96 weeks, until the product is commercially available, or until the Sponsor discontinues development of the product for the prevention of angioedema attacks, whichever comes first. Any subject who discontinues androgen prophylaxis at the time of signing informed consent or at the screening visit will have an additional visit to measure alanine aminotransferase (ALT), aspartate aminotransferase (AST), alkaline phosphatase (ALP), lactate dehydrogenase (LDH), gamma-glutamyltranspeptidase (GGT), and total and direct bilirubin 2 weeks (+7 days) after androgen discontinuation and before initiating treatment with BCX7353.
 
Data from ongoing studies BCX7353-302 (Phase 3 study), BCX7353-301 (Phase 3 study) and the current study, BCX7353-204, are reviewed by the BCX7353 data monitoring committee (DMC) at protocol-specified intervals. The DMC may also be convened if a new clinically significant safety signal emerges or at other times as requested. The latest data review was conducted on 31 July 2019. The recommendation of the DMC was that all 3 studies proceed per protocol.

Study drug will be discontinued for subjects who are deriving no clinical benefit, are intolerant of study drug, or experience an unacceptable drug-related adverse event (AE). The study will be discontinued if ongoing regulatory or institutional review board/ethics committee approval is withdrawn, or in the event that technical or logistical factors prevent the ongoing conduct of the study. Safety and tolerability will be evaluated through assessments of AEs, laboratory analyses (clinical chemistry, hematology, coagulation and urinalysis), vital signs, electrocardiograms (ECGs), and physical examinations.

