5.4.4. Rationale for Allowance and Restriction of Concomitant Medications for HAE

All subjects must have access to appropriate treatments for the treatment of acute attacks (ie, icatibant, plasma-derived C1-INH [any form]), ecallantide, recombinant C1-INH). Each subject will continue to use their prescribed acute medication to treat any attacks, under the medical management plan advised by their physician, throughout the study. This is consistent with guidance documents that strongly support the position that all subjects with C1-INH deficiency should have access to medications for treating attacks (Cicardi, Bork et al. 2012, Zuraw, Banerji et al. 2013).

While there are approved therapies in many countries for prophylaxis against HAE attacks, including C1-INH infused intravenously, consensus recommendations do not exist for either a standard of care for prophylactic treatment or a definition of indications for prophylaxis. A guideline published on the management of HAE by the US HAE Association Medical Advisory Board suggests that decisions on when to use prophylaxis should be individualized (Zuraw, Banerji et al. 2013):

‘The decision about when to use long-term prophylactic treatment cannot be made on rigid criteria but should reflect the needs of the individual patient. Decisions regarding which patients should be considered for long-term prophylaxis should take into account attack frequency, attack severity, comorbid conditions, access to emergent treatment, and patient experience and preference.’

Subjects may receive prophylactic therapies (eg, C1-INH, tranexamic acid, lanadelumab). Investigators may make modifications to the dose and schedule of the prophylactic therapy, including tapering or discontinuation of dosing, according to the degree of benefit of daily oral BCX7353 treatment. Recommended strategies for switching to BCX7353 prophylaxis from another therapy are provided in Section 9.7.

Androgen use, however, is prohibited within 28 days of the baseline visit and at any time during the study to reduce the incidence of transaminase elevations (see Section 9.7.1).

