**Table 2: Protocol Revision Chronology**

Protocol	Date	Key Information
Protocol Version 1.0	20 September 2017	Original
Protocol Version 2.0	5 December 2017	Made administrative clarifications, changed design to include 2 dose groups, increased sample size, removed option to reduce dose, AECT assessment removed, updated prohibited medications
Protocol Version 3.0	6 December 2017	Made administrative clarifications, expanded inclusion criteria to include subjects naïve to BCX7353 in selected countries
Protocol Version 4.0	5 October 2018	Made administrative clarifications, expanded subject numbers, expanded inclusion criteria, extended study duration to 96 weeks, added study data, and clarified discontinuation criteria
Protocol Version 5.0	7 February 2019	Expanded subject numbers, added US sites, added subjects with recent androgen use.

Abbreviations: AECT = Angioedema Control Test; US = United States.

This SAP was developed in accordance with International Council for Harmonisation (ICH) E9 guideline. The purpose of this document is to provide details on the statistical methodology used to analyze the safety and effectiveness for Study BCX7353-204. Study population definitions, derivations of variables, handling of missing data, and other information necessary for analysis of study data are provided. Planned tables, figures, and listings are specified. All decisions regarding final analysis, as defined in this SAP document, will be made prior to database lock of the study data. Further information can be found in the protocol and electronic Case Report Forms (eCRFs).

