## 6. GENERAL CONSIDERATIONS FOR DATA ANALYSES AND HANDLING

### 6.1. General Summary Table and Individual Subject Data Listing Considerations

Tables and listings will be prepared in accordance with the current ICH Guidelines (ICH E3 Structure and Content of Clinical Study Reports 1996). The information and explanatory notes in the “footer” or bottom of each table and listing will include the following information:

- Date of data extraction
- Date of output generation
- Statistical Analysis Software (SAS®) program name, including the path where the program is stored
- Any other output specific details that require further elaboration

In general, tables will be formatted with columns displaying findings for all subjects by treatment group and all subjects across treatment groups.

Version 9.4 or higher of the SAS system will be used to analyze the data and to generate tables, figures, and listings. All SAS programs prepared to analyze the data will be properly annotated so as to permit uninvolved outside statistical experts to replicate all the analyses specified in this SAP.

These listings will generally be sorted by treatment group, subject identifier, and visit, if applicable.

Summary displays will be presented by treatment. A column that combines both active treatments will also be included. [Table 4](#) shows treatment descriptors for displays.

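### If the later 150 mg-only US subjects join the existing 150 mg column, the overall safety columns cannot separate dose from protocol stage, androgen washout, region, visit schedule and background prophylaxis

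*SAP*

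**What the plan says.** **Columns.** SAP 6.1 states: "Summary displays will be presented by treatment. A column that combines both active treatments will also be included". Table 4 of the SAP lists three columns: 110 mg, 150 mg and Total. Protocol 13.3.5 also summarises safety by treatment group.

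**Allocation.** SAP 4.4 describes central allocation and mentions no randomisation. Which doses a site could use depended on its protocol version: "sites initiated under protocol Version 1 have all subjects allocated to the 150 mg dose". Versions 2 and 3 allowed either dose. For the next two versions the SAP says: "No changes to the allocation scheme were made in Protocol Versions 4 and 5".

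**Scope of the SAP.** SAP Table 2 ends at Version 5.0, described as "Expanded subject numbers, added US sites, added subjects with recent androgen use". SAP 4.3.1 plans about 225 subjects, about 110 per dose.

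**The later stage.** The protocol synopsis lists "Protocol Versions 5.0, 6.0, 8.0, 9.0: Multiple centers in the United States (US) only" and assigns 150 mg once daily to subjects enrolled under Versions 6.0 and 9.0. Protocol 13.1 plans about 475 subjects in all, about 250 in the US. Protocol 5.4.4 states: "Androgen use, however, is prohibited within 28 days of the baseline visit and at any time during the study". On-treatment visits are at Weeks 4, 12, 24, 48, 72 and 96 (Protocol 7). SAP 4.1 has eleven on-treatment visits, including a Week 2 visit that its Table 3 reserves for liver function tests.

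**Existing stratification.** SAP 9.2 defines safety subgroups by time since stopping androgens and by duration of androgen use. SAP 9.3.1 repeats the TEAE tables, and 9.6 the hepatic laboratory display, within them.

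**The concern.** The 110 mg column can only come from versions that offered 110 mg. The 150 mg column would hold those versions' 150 mg subjects plus a later group with a different androgen rule, country, visit schedule and pattern of prophylaxis. Protocol 5.4.3 says the trial had so far run mainly outside the US, often where long-term prophylaxis is uncommon, whereas it is prevalent in the US.

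Transaminase elevation is one of two important potential risks named in Protocol 5.7, and Protocol 5.2.2 shows it concentrated in subjects who stopped androgens shortly before dosing. A difference between the overall columns, or the lack of one, could therefore reflect who was enrolled and how often they were tested. Protocol 5.7 already describes the ALT/AST increases as not dose dependent, so readers do draw dose conclusions from this programme's data.

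**Working it through.** **Inputs**
- Interim N (Protocol 5.2.2): 100 on 110 mg and 127 on 150 mg, total 227.
- Androgen history (same section): 40 stopped within 2 weeks of the first dose, 113 stopped earlier, 74 never used. 40 + 113 + 74 = 227, which agrees.
- ALT > 3 × ULN: 32.5% of the recent stoppers, and 15 subjects in all.
- ALT-increased TEAEs: 25.0%, 2.7% and 1.4% in the three groups.
- Planned total: about 475 (Protocol 13.1), so 475 − 227 = 248 later subjects.

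**Reproducing the protocol's figures.** 13/40 = 32.5%. 10/40 = 25.0%, 3/113 = 2.7%, 1/74 = 1.4%.

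**Rates by stratum.** Outside the recent-stopper stratum there are 227 − 40 = 187 subjects.
- ALT > 3 × ULN: recent p1 = 13/40 = 32.5%; others p0 = (15 − 13)/187 = 1.1%; overall 15/227 = 6.6%.
- ALT-increased TEAE: p1 = 25.0%; p0 = (3 + 1)/187 = 2.1%; overall 14/227 = 6.2%.

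**Assumptions.** There is no dose effect within either stratum. All 248 later subjects take 150 mg, none is a recent stopper, and they have rate p0.

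**Formula.** Let r of the 40 recent stoppers be on 110 mg. After the later subjects are added, the 150 mg column holds 127 + 248 = 375.
- 110 mg column = [r·p1 + (100 − r)·p0] / 100
- 150 mg column = [(40 − r)·p1 + (335 + r)·p0] / 375

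**Proportional split.** r = 40 × 100/227 = 17.62, leaving 22.38 on 150 mg.
- ALT > 3 × ULN: 110 mg = (17.62 × 0.325 + 82.38 × 0.0107)/100 = 6.6%; 150 mg = (22.38 × 0.325 + 352.62 × 0.0107)/375 = 2.945%, or 2.9%. Gap −3.7 points.
- ALT-increased TEAE: 110 mg = (17.62 × 0.25 + 82.38 × 0.0214)/100 = 6.2%; 150 mg = (22.38 × 0.25 + 352.62 × 0.0214)/375 = 3.5%. Gap −2.7 points.

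**Other splits.** The documents do not give r, so the whole range is shown for ALT > 3 × ULN:

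| r on 110 mg | 110 mg | 150 mg, interim | 150 mg, with later subjects | Gap (150 − 110), interim → final |
|---|---|---|---|---|
| 0 | 1.07% | 10.97% | 4.42% | +9.90 → +3.35 |
| 10 | 4.21% | 8.49% | 3.58% | +4.28 → −0.63 |
| 17.6 | 6.61% | 6.61% | 2.95% | 0.00 → −3.66 |
| 25 | 8.93% | 4.78% | 2.33% | −4.15 → −6.60 |
| 40 | 13.64% | 1.07% | 1.07% | −12.57 → −12.57 |

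Under these assumptions the later subjects lower the 150 mg column or leave it unchanged, but the sign of the final gap depends on r. With k recent stoppers on 150 mg, the columns are equal when k/375 = (40 − k)/100, so k = 15,000/475 = 31.6. The 150 mg column reads lower unless at least 32 of the 40 took 150 mg; a proportional split gives about 22. Using 250 later subjects instead of 248 moves no gap by more than 0.02 points. Within an androgen-latency stratum the gap is zero by construction.

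**What cannot be computed.** The documents give no liver data by region, visit schedule or background prophylaxis. The visit counts are 11 in the SAP and 6 in the current protocol, so later subjects have fewer scheduled chances to show an elevation.

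**The case against.** The strongest reply is that the SAP already separates washout. A subject with at least 28 days off androgens cannot fall in the under-2-weeks stratum, and both the TEAE and the hepatic tables are repeated by latency. For liver events this stands, and it removes most of the effect illustrated above. It does not change the overall columns, and it does not separate region, visit schedule or protocol stage. Country and site appear in the disposition summaries, not the safety tables. For background prophylaxis, SAP 9.3.1 plans a single TEAE table for subjects taking prophylaxis alongside study drug, with no matching table for the others.

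A second reply is that the SAP predates the 150 mg-only stage and never says those subjects join the column. That also stands, and it makes the point conditional. But the current protocol keeps summaries by treatment group, and no document says how the later subjects will be shown.

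A third reply is that no hypothesis tests are planned. That limits the stakes, but descriptive columns are still read as dose comparisons.

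A reader might go further and infer that the columns will differ because of washout and region rather than dose, making 150 mg look safer for the liver. The documents do not support this. They give no liver rates by dose or region and no dose split of the 40 recent stoppers. The interim remarks on dose concern overall adverse events and gastrointestinal events in the 227 subjects at the August 2019 cut-off, before any such pooling. Nor can all later US subjects be taken as 150 mg with a 28-day washout. Version 5.0 was also a US version and kept the two-dose allocation, the synopsis does not name Version 8.0 in its dose statement, and the washout rule in Versions 6.0 and 8.0 is not shown.

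**Conclusion.** The point holds in a conditional form. If subjects from the 150 mg-only stage enter the existing 150 mg column, the overall columns cannot separate dose from protocol stage, washout, region, visit schedule and background prophylaxis. Washout is largely handled for liver events by the latency tables; the other factors are not.

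The size is illustrative. With no dose effect and a proportional split, the columns would read 6.6% against 2.9% for ALT > 3 × ULN and 6.2% against 3.5% for ALT-increased TEAEs. Over all splits the first gap runs from +3.35 to −12.57 points, so neither its direction nor its size is established. The result rests on equal within-stratum rates at both doses, no recent stoppers among the later subjects, and the interim rate outside that stratum carrying over to them.

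**What to change.** Update the SAP beyond Version 5.0 and state how the later subjects are displayed. In SAP Table 4, show 150 mg as:
- (a) subjects enrolled while both doses were open at their site;
- (b) subjects enrolled when only 150 mg was available, with Version 1 sites and the later 150 mg-only versions shown separately;
- (c) 150 mg total.

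Classify by the doses open at the site on the enrolment date, because SAP 4.4 says some Version 1 sites later changed version. Limit any 110 versus 150 mg reading to (a) against the 110 mg column, and read liver events within androgen-latency strata. Footnote that allocation was not randomised and differed by site and version.

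Because the latency strata then carry the liver reading, SAP 6.7.4 should also be tidied. It subtracts the treatment start date from the last androgen date, which is negative for anyone who stopped before dosing.

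This is a cheap improvement: one derived variable and a few extra columns. The downside is wider tables and smaller cells.

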## **4.5. Assessments**

The schedule of assessments is provided in [Table 3](#).

**Table 3: Schedule of Clinical Assessments**

Assessment	Screening Period	Baseline Visit a	Treatment Period (Visit schedule)					End of Study Assessment
	Screening Visit (Up to Day -28)	(Day 1)	Week 2 (Day 15 ± 2 days) b	Week 4 (Day 29 ± 2 days)	Week 8 (Day 57 ± 2 days)	Week 12 (Day 85 ± 2 days)	Visits every 12 weeks until 96 weeks (± 6 days)	3 weeks (± 3 days) after last dose of study drug
Informed consent c	X	X						
Clinic staff phone call/ communication							X d	
Inclusion-exclusion criteria	X	X						
Medical and medication history, HAE medical and medication history e	X	X						
Weight/height/BMI f	X	X		X	X	X	X	X
Drugs of abuse screen g	X							
Physical examination h	X	X		X	X	X	X	X
Pregnancy test i	X	X		X	X	X	X	X
Vital signs j	X	X		X	X	X	X	X
FSH k	X	X						
HIV, HCV, HBV serology	X							
Diagnosis of HAE established l	X							
Clinical chemistry/hematology/coagulation g	X	X	X b	X	X	X	X	X
Troponin I and Troponin T, CK-MB		X		X	X	X	X	X
NGAL and ACR		X				X	X	X
Urinalysis g	X	X	X b	X	X	X	X	X

b The Week 2 visit will consist of monitoring liver function tests only [ALT, AST, GGT, total and direct bilirubin, ALP]; urine and additional tubes of blood may be required to accommodate reflex testing for abnormal GGT (see protocol Table 7). If preferred by the subject and clinical site, laboratory values may be drawn and resulted locally, with results entered into the CRF.

c Informed consent will be signed at the screening visit for subjects requiring a screening visit and will be signed for all other subjects at the baseline visit or final on treatment visit in the parent study (which serves as the subject's baseline visit in this study).

d After the Week 12 visit, clinic staff must contact the subjects at least once every 4 weeks between clinic visits to assess the subject's overall wellbeing and any issues with regards to study drug tolerability. During all calls, sites will also discuss study drug compliance and any issues with the diary or study drug.

e Medical history and medication history will be completed at screening (for subjects requiring a screening visit) and at baseline. At the Screening visit (or baseline for those with no screening visit), the HAE Medical and Medication history form will be updated from the previous HAE study, as applicable, with additional questions to be answered if provided.

f BMI calculation and height at screening; weight is to be recorded at each in-clinic visit.

g Please see protocol Table 7 for analytes to be assessed. The lipid panel as part of clinical chemistry will only be measured at baseline, Week 12 and then every 12 weeks.

h Full physical examinations will be performed at screening and baseline; symptom-directed physical examinations will be performed at all post-baseline visits.

i For women of childbearing potential, a serum pregnancy test will be administered at screening, urine pregnancy tests will be assessed at all subsequent visits as indicated in the table. Demonstration of a negative urine pregnancy test will be required prior to dispensing study drug.

j To include blood pressure and pulse rate. Temperature and respiratory rate will be captured at screening and baseline only. Prior to obtaining vital signs, subjects should rest in a supine position for at least 5 minutes.

k For a woman who declares that they have been post-menopausal  $\leq 2$  years or was considered a woman of childbearing potential in the previous study. The sample may be drawn at baseline for those who do not undergo a screening visit; however, the subject must have a negative urine pregnancy test at baseline prior to receiving study drug.

l For subjects that have not participated in a previous BCX7353 study, a clinical diagnosis of hereditary angioedema Type 1 or Type 2, defined as having a C1-INH functional level below 50% and a C4 level below the lower LLN reference range, as assessed during the Screening period. In the absence of a low C4 value drawn during the inter-critical period, one of the following is acceptable to confirm the diagnosis of HAE assessed during the Screening period: 1) a SERPING-1 gene mutation known or likely to be associated with HAE Type I or II; 2) a confirmed family history of C1-INH deficiency; 3) a C4 redrawn and retested during an attack with the results below the LLN reference range.

m A sample for HLA analysis will be drawn on subjects who have not donated one in a previous study. The sample may be drawn at baseline or at any subsequent visit.

n All ECGs during the study will be single assessments with the exception of baseline which will be obtained in triplicate. An ECG should be repeated for a change from baseline in QTcF  $> 60$  msec or a QTcF interval  $> 500$  msec. Prior to obtaining an ECG, subjects should rest quietly in a supine position for at least 10 minutes.

o AE-QoL and TSQM will be administered once at baseline and at Weeks 4, 8, 12, and every 12 weeks thereafter. Additional questions regarding loss of time from work/school will be instituted at each visit to more fully characterize QoL.

p Concomitant medications will be reviewed at each visit and on treatment, new concomitant medications will be reviewed to determine whether there are any contraindications or dosage adjustments required.

q The actual date and time of PK blood draw, and time of last study drug dose (relative to PK sample draw) will be captured in the CRF.

r Site staff will review the diary instructions with the subjects at the first clinic visit. Subjects will be instructed to bring the completed diary with them to their visits. Any issues with the entered data in the diary will be discussed with the subject and corrections will be made by the subject as required.

s Sites will request a treatment allocation in the IXRS for eligible subjects at the Day 1 visit

t At any time the diary is in a subject's possession, they will enter HAE attacks and relevant details and dosing information (as applicable) once per day.

